activity against genotypes 1 through 6 and a high genetic barrier to resistance, with no or little loss of potency against common resistant-associated substitutions. G/P is co-formulated Glecaprevir 100 mg and Pibrentasvir 40 mg as a fixed-dose combination tablet, which provides patients with a convenient treatment regimen of three tablets once daily to be taken with food.¹⁰

Expedition 4 was an international, open-label Phase 3 study of 12 weeks of G/P in 104 patients with eGFR < 30mL/min/1.73m² including 85 patients on dialysis and 19 with pre-dialysis chronic kidney disease (CKD). By intention to treat analysis 102/104 patients were cured and there were no virologic failures (1 treatment discontinuation due to diarrhea and 1 died of unrelated causes). Also, there were no treatment-related serious adverse events.¹¹

G/P has multiple advantages in the solid organ transplantation context. G/P is the only DAA regimen that is appropriate to administer among dialysis patients or in the immediate post-kidney transplant period (where a substantial proportion of deceased donor transplant recipients have delayed graft function)¹² that is effective against all genotypes of HCV.¹³ Furthermore, G/P 300mg/120mg once daily given for 12 weeks has also been studied in 100 patients with chronic HCV infection post liver (n=80) or kidney transplantation (n=20). The overall SVR12 rate was 98% (98/100) with 1 post liver transplant patient experiencing virologic relapse and one patient was lost to follow-up. The most common adverse events in >10% of patients included headache, fatigue, nausea, pruritus, and diarrhea. There were two serious AEs deemed related to G/P including sinusitis and abnormal hepatic function at post-treatment week 4. There was one AE, a cerebrovascular accident that led to study drug discontinuation at week 6 of treatment and the patient achieved SVR12. Subjects were on the following immunosuppressant medications Tacrolimus (n=68), Mycophenolate mofetil (n=30), Cyclosporine (n=13), Prednisone (n=13), Everolimus (n=8), Azathioprine (n=6), and Sirolimus (n=7)¹⁴.

The results of the THINKER trial provided preliminary evidence that HCV-infected organs could be safely transplanted into recipients who do not have HCV infection, and the virus

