Clinical outcomes post-transplant will include death, graft failure, acute allograft rejection, delayed graft function, ALT elevation > 5 times the upper limit of normal, and SAEs. In addition, HCV-infection related events of fibrosing cholestatic hepatitis and extrahepatic manifestations of HCV infection collected for Arm 1 subjects and only for Arm 2A subjects who develop HCV viremia will also count as clinical outcomes. The number and percentage of subjects with each and any clinical outcomes will be summarized for those who receive an HCV RNA-positive kidney (Arm 1) versus Arm 2 subjects combined and broken down (2A and 2B) as applicable. The difference in the overall percentage of subjects with clinical outcomes post-transplant in Arm 1 vs Arm 2A + 2B will be assessed by logistic regression with Arm as a factor and including appropriate covariates to adjust for possible differences between Arms including waiting list priority, blood group,

geographic region and sensitization, as appropriate given sample size and other statistical considerations. In addition, to include any clinical outcomes due to being treated with G/P, another summary of clinical outcomes post-transplant will include any study drug (G/P) related severe treatment emergent adverse events for Arm 1 subjects, and another will include events of treatment emergent Grade ≥ 3 laboratory values and related severe treatment emergent adverse events as clinical outcomes for Arm 1 subjects.

Analyses of the eGFR outcome will be calculated eGFR using the 4-variable MDRD equation. Mean (SD) eGFR will be summarized at appropriate visits and compared between Arms. Specifically, mean eGFR at 24 weeks/6-months post-transplant and 1 year post transplant will be compared between Arm 1 transplant recipients and the combined group of Arm 2A and 2B transplant recipients (2B1-2B4). As a secondary approach, mean eGFR at 24 weeks/6-months post-transplant will be compared between Arm 1 recipients and Arm 2A and 2B kidney recipients limited to those 2A and 2B recipients who did not develop HCV infection.

We will also compare estimated proteinuria between Arms 1 and 2A, including a count of individuals with >1000 mg/day estimated proteinuria. Proteinuria will be estimated using spot protein:Cr ratio.

An exploratory analysis will summarize the number and percentage of subjects with clinical outcomes post kidney transplant for the subgroups of Arm 2B.

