Exploratory analyses will also make comparisons between groups in which recipients of non study-eligible HCV RNA-positive and non study-eligible RNA-negative/HCV Ab-positive kidneys are censored at transplantation.

These clinical outcomes post-transplant will be further summarized by relatedness to study drug or HCV infection for Arm 1 subjects, and relatedness to transplant for each group Arm 1, Arm 2A, and Arm 2B subjects.

In addition, for subjects in study Arm 2 receiving HCV antibody-positive/ HCVRNA-negative kidneys, the rate and timing of HCV transmission will be summarized.

8.1.5 Safety Analyses for Arm 1

Adverse events will be coded using the Medical Dictionary for Regulatory Activities (MedDRA). Subjects reporting more than one adverse event for a given MedDRA preferred term will be counted only once for that term using the most severe grade for the severity grade table and the most related for the relationship to study drug table. Subjects reporting more than one type of event within a SOC will be counted only once for that SOC. An adverse event will be considered treatment-emergent if it begins or worsens in severity after initiation of study drug through 30 days post-study drug dosing. Related adverse events are those considered at least possibly related to study.

Laboratory data will be summarized from the first dose of G/P through 2 days post dosing. Laboratory values will be rated according to the National Cancer Institute Common Terminology Criteria for Adverse Events (NCI CTCAE Version 4) which is available on the Cancer Therapy Evaluation Program (CTEP) website at:
http://evs.nci.nih.gov/ftp1/CTCAE/CTCAE_4.03_2010-06-14_QuickReference_8.5x11.pdf
Grade 3+ laboratory values are those that are Grade 3 or 4.

8.1.6 Additional Adverse Event Analyses for Arm 1

For subjects treated with G/P, the number and percentage of subjects with treatment-emergent adverse events (i.e., any event that begins or worsens in severity after initiation of study drug through 30 days post-study drug dosing) will be tabulated by primary MedDRA System Organ Class (SOC) and preferred term (PT) for each treatment arm. The tabulation of the number of subjects with treatment-emergent adverse events by severity grade and relationship to study drug, kidney transplantation, or HCV infection also will be provided.

8.1.7 Additional Clinical Laboratory Data for Arm 1

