Clinical laboratory tests will be summarized by transplant phase (e.g., awaiting a transplant, after receipt of a transplant) and treatment arm. Additional evaluations will be performed for subjects who received study drug as part of the protocol (Arm 1). The baseline value will be the last non-missing measurement prior to the initial dose of study drug. Mean changes from baseline to each post-baseline visit, including the Final Treatment Visit, will be summarized descriptively for Arm 1 as feasible.

In addition, the number and percentage of subjects with post-baseline laboratory values of interest equal or greater than Grade 3 of the CTCAE scale will be summarized overall and by Arm.

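### The Grade 3 or higher laboratory count in Arm 1 does not require worsening from the pre-dose grade, and treatment-emergent is not defined for laboratory values

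*Protocol*

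**What the plan says.** Protocol Section 8.1.7 states the count: "the number and percentage of subjects with post-baseline laboratory values of interest equal or greater than Grade 3 of the CTCAE scale", to be shown overall and by arm. The same section defines a baseline, "The baseline value will be the last non-missing measurement prior to the initial dose of study drug", but applies it only to mean changes.

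Section 8.1.5 gives the window, "Laboratory data will be summarized from the first dose of G/P through 2 days post dosing", and the grading rule, "Grade 3+ laboratory values are those that are Grade 3 or 4". For adverse events, that section has a comparative definition: "An adverse event will be considered treatment-emergent if it begins or worsens in severity after initiation of study drug through 30 days post-study drug dosing". No equivalent sentence covers laboratory values.

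Several places nevertheless call Grade 3 or higher laboratory values treatment-emergent: the Synopsis (additional analyses under secondary endpoint 3), Section 4.2 (objective 3, item b), Section 6.1.4 (HCV Treatment Phase) and Section 8.1.4. In Section 8.1.4, after the main post-transplant outcome analysis, further summaries are added so that effects of G/P treatment are captured. One adds related severe adverse events, and "another will include events of treatment emergent Grade" 3 or higher laboratory values, as outcomes for Arm 1 subjects.

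The SAP has no Grade 3 or higher laboratory analysis. Its nearest item is Part 14, peak ALT above 5 times the upper limit of normal in Arm 1.

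**The concern.** A treatment-emergent laboratory table should separate what appeared or worsened on the drug from what the patient brought to the first dose. In this trial many patients may bring something. Entry requires eGFR below 15 ml/min/1.73 m² at consent (Section 5.2.1.1). The first dose is targeted for day 3 after transplant (Section 5.1). Section 3.0 describes this early period as one "where a substantial proportion of deceased donor transplant recipients have delayed graft function". Table 5 schedules chemistry again at treatment week 1. A value that was Grade 3 or above before dosing, and is improving but still Grade 3 at that draw, meets the Section 8.1.7 rule.

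Safety is part of the primary objective (Section 4.1). Two outputs are exposed. The Grade 3 or higher table would mix carried-over and new abnormalities, so a few new cases could go unnoticed among the old ones. The extended outcome summary in Section 8.1.4 adds these values in Arm 1 only, so any carry-over raises the Arm 1 count and no other.

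**Working it through.** The plan gives no expected rate for these laboratory values, so there is no figure to reproduce. The check compares the rules and then illustrates their effect.

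**Step 1. The rules side by side**

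| Item | Adverse events | Laboratory values |
|---|---|---|
| Window | First dose to 30 days after dosing (8.1.5) | First dose to 2 days after dosing (6.1.4, 8.1.5) |
| Comparison with pre-dose state | Must begin or worsen (8.1.5) | None stated (8.1.5, 8.1.7) |
| Treatment-emergent defined? | Yes (8.1.5) | Term used (Synopsis, 4.2, 6.1.4, 8.1.4), not defined |
| Pre-dose baseline defined? | Not applicable | Yes, for mean change only (8.1.7) |

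Two programmers could follow this text and produce different tables. One would count every Grade 3 or 4 value in the window. The other would borrow the adverse-event wording and drop unchanged values.

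**Step 2. Comparative laboratory rules elsewhere in the protocol**

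Section 6.1.8 acts on ALT only when it exceeds 5 times the upper limit and also twice the baseline value. Section 3.1.4 describes ALT findings in the earlier G/P studies relative to nadir. A comparison with an earlier value is therefore already familiar in this protocol.

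**Step 3. Illustration of size**

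Inputs:
- N = 30, the planned number of Arm 1 transplants (Section 5.1.5).
- p, the share of subjects with a pre-dose Grade 3 or higher value that persists to at least one post-dose draw. Assumed, 10% to 50%.
- q, the share of the remaining subjects with a new Grade 3 or higher value. Assumed, 3% or 10%.

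Formulas:
- Expected count as written = N × [p + (1 − p) × q]
- Expected new cases only = N × (1 − p) × q
- Difference = N × p

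The second formula takes no re-worsening among the carried-over subjects.

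| p | q | As written | New cases only | Carried over (N × p) |
|---|---|---|---|---|
| 10% | 3% | 30 × 0.127 = 3.8 (12.7%) | 30 × 0.027 = 0.8 (2.7%) | 3 |
| 20% | 10% | 30 × 0.280 = 8.4 (28.0%) | 30 × 0.080 = 2.4 (8.0%) | 6 |
| 30% | 3% | 30 × 0.321 = 9.6 (32.1%) | 30 × 0.021 = 0.6 (2.1%) | 9 |
| 50% | 10% | 30 × 0.550 = 16.5 (55.0%) | 30 × 0.050 = 1.5 (5.0%) | 15 |

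At p = 10%, the chance that at least one subject is carried over is 1 − 0.9^30 = 95.8%.

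**The case against.** **The label.** A reader might infer that the plan reports pre-existing abnormalities as G/P toxicity. It does not say so. Section 8.1.7 calls the values post-baseline, and the sections that say treatment-emergent leave the term open. If the adverse-event definition were carried over, unchanged values would drop out. This stands: the fault is an absolute-grade count beside an undefined term, not a stated misattribution.

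**The size.** A reader might also take a delayed graft function rate of, say, 20% to 40% and conclude that 6 to 12 of 30 subjects would be Grade 3 or higher for creatinine at week 1. The documents give no such rate, do not reproduce the CTCAE cut-offs and do not list the values of interest. The entry eGFR is measured at consent, not before the first dose. That figure also assumes that every such subject is still Grade 3 or higher at week 1. Moreover, Section 8.1.4 already counts delayed graft function as an outcome in all transplanted groups, so for these subjects the any-outcome total would not change. This also stands. It does not help the Grade 3 or higher table itself, or carried-over abnormalities in subjects without another outcome.

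**Other safeguards.** Mean change from baseline, eGFR over time and classification of adverse events by relationship to drug, transplant or HCV all give context, so the laboratory table is not worthless. None of them separates carried-over from new Grade 3 or higher values.

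**The remedy.** Comparing only with the pre-dose grade would miss a subject who is Grade 3 before dosing, recovers to Grade 1 and returns to Grade 3 on G/P. This stands, and the fix below allows for it.

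**Conclusion.** The concern holds as a defect in the counting rule and a gap in definition. As written, Section 8.1.7 counts any post-baseline Grade 3 or 4 value, and neither the protocol nor the SAP requires worsening from the baseline that this section already defines. The timing of the first dose and the entry criteria make carried-over values plausible. How many subjects are affected cannot be derived from the documents. The range of 3 to 15 of 30 is purely an illustration of an assumed 10% to 50% carry-over.

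The consequence is a safety table that can mislead, and an Arm 1 outcome summary that can be raised by abnormalities present before the drug was given. The analysis is secondary and descriptive, and the SVR12 result is unaffected. The change is worth making because it is cheap and uses data already planned.

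**What to change.** 1. In Sections 6.1.4, 8.1.4, 8.1.5 and 8.1.7, define a treatment-emergent Grade 3 or higher laboratory value as one obtained after the first G/P dose, within the existing window, that is CTCAE Grade 3 or higher and whose grade is higher than either (a) the baseline grade, from the last value before the first dose, or (b) the lowest earlier on-treatment grade. Part (b) counts recovery followed by re-worsening.
2. Use this definition for the Arm 1 outcome summary in Section 8.1.4, and list the laboratory values of interest.
3. Keep the count of all Grade 3 or higher values as a supporting line.
4. Add a shift table of baseline grade against worst on-treatment grade, so that subjects at Grade 3 or 4 before dosing remain visible.

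The cost is a few sentences and one table shell, with no new data collection. There is a small downside: a subject at Grade 4 before dosing who never improves cannot become an emergent case and appears only in the shift table and the supporting line.

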8.2 Determination of Sample Size

This study is primarily designed to demonstrate feasibility and to generate preliminary data related to cure rates (defined as SVR₁₂) from treating donor-derived HCV infection post kidney transplantation using G/P. For this reason, the sample size was not determined with reference to power to detect differences between groups for the primary objective. The lower bound of a one-sided 95% confidence interval using the Wilson's score method, for various SVR₁₂ rates with a total sample size of 30 subjects are provided in Table 10.

Table 10: Estimated Lower Bound for 95% Confidence Interval for Cure Rate Based on Observed Number of Cures

Sample Size	No. of Observed Cures	Observed Cure Rate	Lower Bound for 95% CI of Cure (Wilson's Score)
30	30	100.0%	93.8%
30	29	96.7%	85.4%
30	28	93.3%	81.0%
30	27	90.0%	76.9%
30	26	86.7%	73.0%

As a secondary objective, we will compare time to kidney transplantation between the estimated 75 - 90 kidney transplant candidates enrolled in this trial with 225-270 matched kidney transplant candidates from the OPTN list (1:3 match). We estimate that at least 40

patients (44%) of 90 enrolled patients will undergo kidney transplantation versus 20% (or less) of comparators from OPTN list during an estimated 6 months of follow-up, with 80% power to detect a difference between groups.

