The primary efficacy endpoint is sustained virologic response 12 weeks post dosing (SVR₁₂), defined as HCV RNA < LLOQ 12 weeks after the last actual dose of G/P. The SVR₁₂ rate will be determined from all enrolled subjects who received an HCV RNA-positive kidney in Arm 1 and received at least one dose of G/P study drug along with a two-sided 95% confidence interval. The confidence interval for the SVR₁₂ rate will be calculated using Wilson's score method.

The secondary efficacy endpoints for recipients of kidney transplants from HCV RNA-positive donors in Arm 1 are:

1. The percentage of subjects with on-treatment virologic failure;
2. The percentage of subjects with post-treatment virologic relapse.

Additional efficacy analyses will be performed.

Clinical endpoints:

Secondary endpoints for the secondary objectives are:

1. Among all subjects enrolled in the study who receive a kidney transplant, the time to kidney transplant and cumulative incidence of each type of transplant will be determined for: study-eligible HCV RNA-positive kidneys (Arm 1), study-eligible HCV RNA-negative/HCV Ab-positive kidneys (Arm 2A), and standard of care kidney transplants (Arm 2B).
2. The number and percentage of subjects with clinical outcomes while on the

waitlist (SAEs, delisting from waitlist, death) among subjects who receive an HCV RNA-positive kidney in Arm 1 and among those subjects who do not receive a study eligible HCV RNA-positive kidney (all Arm 2 subjects) overall and with breakdown by the category in Arm 2 (2A, 2B and 2C). In addition, the total number of inpatient hospital days while on waitlist in those who did receive a study eligible HCV RNA-positive kidney (Arm 1) and total inpatient hospital days in those who did not (Arm 2) overall and with breakdown by categories of Arm 2 will be summarized descriptively.

3. The number and percentage of subjects with the following clinical outcomes and data post-transplant as applicable: death, graft failure, acute allograft rejection, delayed graft function, ALT elevations > 5x ULN, and SAEs. The difference in the overall percentage of subjects with clinical outcomes and data post-transplant between Arm 1 and Arms (2A + 2B1 – 2B4) will be assessed by logistic regression with Arm as a factor and appropriate covariates to adjust for possible differences between Arms including waiting list priority, blood group, geographic region and sensitization as appropriate.

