8.1 Statistical and Analytical Plans

The data analysis will be generated using SAS version 9.4 or higher for windows and/or STATA software version 14.0 or higher (StataCorp LP, College Station, TX). SAS Institute Inc. SAS and all other SAS Institute Inc. product or service names are registered trademarks or trademarks of SAS Institute Inc., Cary, NC, USA. All statistical tests (if applicable) and confidence intervals will be two-sided with an alpha level of 0.05.

Descriptive statistics will be provided, such as the number of observations (N), mean, and standard deviation (SD) for continuous variables and counts and percentages for discrete variables.

The efficacy and safety of the “reactive” G/P treatment of patients who become HCV RNA-positive after receiving a kidney from a study eligible HCV RNA-negative/HCV Ab-positive donor in Arm 2A are not an objective of this study, and they are not included in assessments of efficacy or safety described below. The time to transplant and clinical outcomes and data post-transplant from patients in Arm 2A are included in those secondary endpoints.

The primary analysis will occur after all recipients of HCV RNA-positive kidneys in Arm 1 have completed post-treatment week 12 visit (corresponding to SVR₁₂ data collection) or prematurely discontinued study. The primary analysis of SVR₁₂ will be performed on the intention-to-treat (ITT) population defined as all enrolled subjects who received a study eligible HCV RNA-positive kidney and received at least one dose of G/P according to actual treatment received (Arm 1).

No data will be imputed for any efficacy or safety analysis except for analyses of SVR endpoints (HCV RNA data). HCV RNA values will be selected for the analyses of all SVR endpoints (e.g., SVR₄ and SVR₁₂, SVR₂₄) based on defined visit windows. A backward imputation method will be used to impute missing responses for SVR analyses. Additional details of analyses to be performed will be specified in the Statistical Analysis Plan.

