8.1.2.1 Primary Efficacy Endpoint

The primary efficacy endpoints is the proportion of ITT subjects who achieved SVR₁₂ (HCV RNA < LLOQ 12 weeks after the last actual dose of study drug).

The number and percentage of subject achieving SVR₁₂ will be summarized along with a two-sided 95% confidence interval calculated using Wilson's score method. A summary of reasons for SVR₁₂ non-response (e.g., on-treatment virologic failure, relapse, other) will be provided.

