8.1.2.4 Subgroup Analysis

The percentage of ITT subjects with SVR₁₂ will be calculated, as will the corresponding two-sided 95% Wilson score intervals by the following subgroups:

- HCV GT
- Timing of HCV treatment initiation after transplant
- Study drug compliance

Further details about subgroup analyses will be described in the Statistical Analysis Plan

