8.1.2.5 Additional Efficacy Endpoints

The following additional efficacy endpoints will be summarized for the ITT population:

- The percentage of subjects with HCV RNA < LLOQ at each post-baseline visit in the Treatment Period (using data as observed);
- The percentage of subjects with SVR4;
- The percentage of subjects with SVR24 and the concordance between SVR12 and SVR24

In the above analyses for SVR, the percentage of subjects and a two-sided 95% Wilson score interval will be summarized.

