Summary of Statistical Analysis Plan for MYTHIC Study

[Draft: April 26, 2020]

Part	Patient Group(s)	Outcome	Statistical Analysis ^a
1	Arm 1 (ITT)	SVR12	- estimated probability of SVR12 and 95% confidence interval (CI) - exact binomial calculations
2	Arm 1 (ITT)	Virologic failure (VF)	- estimated probability of SVR12 and 95% confidence interval (CI) - exact binomial calculations
3	Arm 1 (ITT)	Post-treatment virologic relapse	- estimated probability of SVR12 and 95% confidence interval (CI) - exact binomial calculations
4	All patients	HCV-viremic kidney transplant (KT); i.e., Arm 1 KT	- cumulative incidence and 95% CI - death and other KT types treated as competing risk - estimate non-parametrically, using Lin (1997) which proceeds through the cause-specific hazards, or Fan (2013) which uses Inverse Probability of Censoring Weighting (IPCW).
5	All patients	Non-HCV-viremic KT; i.e., Arm 2A-2B KT	- same as for component (4).
6	All, by Arm	Hospital admissions	- Arm treated as a time-dependent treatment - crude hospitalization rate per 100 patient-years (PY) and 95% CI - use robust variance estimator, to account for correlation among hospital admissions within-patient
7	All, by Arm	Hospital admissions	- Arm treated as a time-dependent treatment - proportional rates model (Lin et al., 2000) - robust SEs, to account for clustering within-patient
8(a)	All, and SRTR* controls	Kidney transplant	- exclude, from SRTR, all patients who indicated consent to receive an HCV-viremic KT (hereafter: SRTR*) - estimate prognostic score using SRTR* patients: KT as event - 1:5 matching (MYTHIC : SRTR*) based on prognostic score with caliper - Cox regression, with MYTHIC as lone covariate, stratified by matched set

8(b)	All, and SRTR* controls	Kidney transplant	Same as 9(a), but using exact matching on small set of predictors, with prognostic score used to break ties among potential matches
9	Arm 1 – ITT	Compliance	Treated as repeated binary (0/1) data, with 1 indicating compliance (i.e., having taken 80-120% of prescribed pills)
10	Arm 1 – ITT	Death	Time to event; Cox regression
11	Arm 1 – ITT	Graft failure	Time to event; Cox regression
12	Arm 1	Delayed graft function	DGF: binary (0/1) response. Compute OBS/EXP, where OBS=observed number of DGFs for Arm 1 and EXP= expected count based on logistic regression model fitted to HCV-negative UNOS patients from large academic centers

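### Table 10's lower bounds are not the one-sided 95% Wilson bounds they are labelled as; the planned SVR12 interval is two-sided; and the SAP names exact limits where the protocol names Wilson

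*Protocol*

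**What the plan says.** **Table 10.** Section 8.2 states that the sample size was not set by power and offers Table 10 instead. The sentence above the table describes its contents as "The lower bound of a one-sided 95% confidence interval using the Wilson's score method", for n = 30. The table's title and column header say only 95% and Wilson.

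**The planned interval.** The synopsis reports the SVR12 rate in Arm 1 subjects who "received at least one dose of G/P study drug along with a two-sided 95% confidence interval" and names Wilson's method for it. Section 8.1 sets the general rule that "confidence intervals will be two-sided with an alpha level of 0.05". Section 8.1.2.1 specifies for the primary endpoint a "two-sided 95% confidence interval calculated using Wilson's score method". The same method is carried into section 8.1.2.4 ("two-sided 95% Wilson score intervals by the following subgroups") and, for SVR4 and SVR24, section 8.1.2.5 ("a two-sided 95% Wilson score interval will be summarized").

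**The SAP.** The SAP summary, marked as a draft of April 2020, lists a 95% interval for SVR12 in Part 1 by "exact binomial calculations". It does not mention Wilson. Parts 2 and 3 have virologic failure and post-treatment relapse in the outcome column, but their analysis column still gives the probability of SVR12 as the quantity to estimate.

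**The concern.** There are three separate problems.

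1. **Arithmetic.** The label fixes the method, the level, the sidedness and n, so each cell can be checked without any outside assumption. The printed cells fail that check, and not all in the same direction.
2. **Sidedness.** The table is one-sided and the planned analysis is two-sided. Even a correctly computed one-sided column would not show the precision of the interval to be reported.
3. **Method.** The two documents name different intervals for the same primary endpoint. If the SAP stands as written and the protocol's other analyses are carried forward, the overall SVR12 rate gets an exact interval while its subgroups, SVR4 and SVR24 get Wilson intervals.

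Because the size is not justified by power, Table 10 is the only statement of how precisely 30 subjects will estimate the cure rate. The worst row is also a likely one. Section 3.2 cites an overall SVR12 rate of 98% from the registration program and suggests similar rates here. If the true rate were 98% (an assumption), 30 cures out of 30 would have probability 0.98^30 = 0.55.

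**Working it through.** **Inputs.** n = 30 and x = 30, 29, 28, 27, 26 (Table 10); one-sided 95%, z = 1.645, z² = 2.706 (section 8.2); two-sided 95%, z = 1.960, z² = 3.841 (sections 8.1 and 8.1.2.1); exact limits (SAP Part 1), read as Clopper-Pearson.

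**Formulas.** With p = x/n:

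- Wilson lower bound = [p + z²/(2n) − z·sqrt(p(1−p)/n + z²/(4n²))] / (1 + z²/n). At x = n this reduces to n/(n + z²).
- Exact two-sided lower limit = the 0.025 quantile of Beta(x, n − x + 1). At x = n this is 0.025^(1/n).

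**Attempt to reproduce the table under its own label.**

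- 30/30: 30/(30 + 2.706) = 91.7%. Printed: 93.8%.
- 29/30: p = 0.96667. Numerator: 1.01176 − 1.645 × sqrt(0.0010741 + 0.0007515) = 1.01176 − 0.07028 = 0.94148. Denominator: 1.09018. Result: 86.4%. Printed: 85.4%.

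The figures are not reproduced.

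**Planned two-sided interval at 30/30.** Wilson: 30/(30 + 3.841) = 88.6%. Exact: 0.025^(1/30) = 88.4%.

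**All rows (lower bounds, %).**

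| Cures | Printed | One-sided Wilson | Two-sided Wilson | Two-sided exact |
|---|---|---|---|---|
| 30 | 93.8 | 91.7 | 88.6 | 88.4 |
| 29 | 85.4 | 86.4 | 83.3 | 82.8 |
| 28 | 81.0 | 81.7 | 78.7 | 77.9 |
| 27 | 76.9 | 77.4 | 74.4 | 73.5 |
| 26 | 73.0 | 73.4 | 70.3 | 69.3 |

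**Printed minus computed, from unrounded values (points).**

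| Cures | vs one-sided Wilson | vs two-sided Wilson | vs two-sided exact |
|---|---|---|---|
| 30 | +2.07 | +5.15 | +5.37 |
| 29 | −0.96 | +2.07 | +2.62 |
| 28 | −0.73 | +2.32 | +3.07 |
| 27 | −0.55 | +2.52 | +3.43 |
| 26 | −0.40 | +2.68 | +3.72 |

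The difference between one-sided and two-sided Wilson is 3.0 to 3.1 points in every row. That part of the second column is due to sidedness. Two-sided Wilson exceeds exact by 0.2 to 1.0 points.

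**What the printed 30/30 value would mean.** Setting 30/(30 + z²) = 0.938 gives z = 1.408, which is one-sided confidence of 92.0%, not 95%.

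**Where the figures may come from.** The four lower rows agree to the printed decimal with one-sided 95% Agresti-Coull bounds (85.37, 81.02, 76.92, 72.99). The same method gives 90.1% at 30/30, not 93.8%. The value 93.8 agrees with a one-sided 90% Agresti-Coull bound (93.78) and with a two-sided 95% likelihood-ratio bound (93.80). These are numerical matches only, since the documents name neither method. Continuity-corrected Wilson, Wald, Jeffreys, mid-P, logit and arcsine intervals, among others, were also tried at tail areas of 0.05, 0.025 and 0.10. No single method at any of these tail areas gives all five rows.

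**The case against.** The strongest reply is that nothing turns on these numbers. Section 8.2 describes a feasibility study, neither document sets an SVR12 success threshold, and the stopping rule in section 5.4.2 counts virologic failures without using a confidence limit. Four of the five rows err by at most 1.0 point against their label, on the conservative side. This stands, and it limits the severity.

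Second, a one-sided planning bound can coexist with a two-sided reported interval, and section 8.2 states the sidedness openly. This also stands in part: about 3 points of each gap to the two-sided bounds is a disclosed choice, so +5.2 at 30/30 is not the size of a calculation error. But the table's own title and header omit the word, and every printed bound, including the four that are conservative under the label, is higher than the limit that will be reported.

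Third, the SAP is a later draft summary, and section 8.1 leaves further analysis details to it, so a deliberate change to exact limits is possible. It neither states nor justifies one, and the protocol had already fixed the method for the primary endpoint. The SAP's wording does not name Clopper-Pearson, so the exact figures here rest on the usual reading. The SAP summary also does not list SVR4, SVR24 or the SVR12 subgroups, so the mixture of intervals arises only if those protocol analyses are run alongside it.

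**Conclusion.** The concern holds and should be fixed. As labelled, Table 10 is wrong in all five rows: 2.1 points too high at 30/30, and 1.0, 0.7, 0.5 and 0.4 points too low in the others (the 27/30 gap is 0.55 before rounding). Against the planned two-sided Wilson interval every row is too high, by 2.1 to 5.2 points, of which 3.0 to 3.1 points per row reflects sidedness. The conflict between Wilson and exact is a real inconsistency on the primary endpoint, worth 0.2 to 1.0 points in the lower limit.

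The Wilson results depend only on figures and methods stated in the documents; the exact results assume Clopper-Pearson. The sample size, the endpoint and every decision rule are unaffected. The wrong text in SAP Parts 2 and 3 is a minor drafting slip.

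**What to change.** 1. Name one interval method for SVR12 in both documents. The two-sided 95% Wilson interval is the simplest choice, since sections 8.1.2.1, 8.1.2.4 and 8.1.2.5 already use it. If exact limits are preferred, say so in the protocol, decide whether the subgroups, SVR4 and SVR24 follow, and name the exact method.
2. Replace the last column of Table 10 with that method's two-sided lower bounds for 30, 29, 28, 27 and 26 cures. Wilson: 88.6, 83.3, 78.7, 74.4, 70.3%. Exact (Clopper-Pearson): 88.4, 82.8, 77.9, 73.5, 69.3%. Delete *one-sided* from section 8.2. If a one-sided planning bound is kept on purpose, print 91.7, 86.4, 81.7, 77.4, 73.4%, put the sidedness in the table header, and show the two-sided bound beside it.
3. In SAP Parts 2 and 3, give the probability of virologic failure and of relapse as the quantities to estimate.

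The cost is five table cells, one word in section 8.2, one method name in the SAP and two wording corrections. It should be settled before the SVR12 results are known, so that the reported limit is not chosen afterwards.
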